231 community dwelling older adults (men or women \geq 65 years) and reporting a loss of physical function over the last six-twelve months and considered at risk of mobility disability will be included in the randomized interventional clinical trial SARA-INT (with 64 patients per treatment group) with a treatment period of 26 weeks. 39 additional participants will be randomized to allow 20% of non-evaluable withdrawals or lost to follow-up for a total of 231 older adults included in the US and the EU.

An unblinded 'promising zone' interim analysis will take place, based on the complete efficacy data from half of the randomized participants who completed the trial, to determine if there will be a need to increase the sample size.

A predefined subgroup efficacy analysis will also be performed in a number of pre-identified, at-high risk of worsening subpopulations:

- Low gait speed
- Sarcopenic obesity
- Study participants with a chair stand sub-score of ≤2 of the SPPB
- Study participants who experience a deterioration in their ALM/BMI, as measured by the DEXA scan, in the M6 visit compared to the baseline measurement

Subgroup analyses on these populations will be performed in order to better characterize treatment benefit in patients at increasing risk of mobility disability. Results will be presented in forest-plot graphs, for the primary and the two key secondary endpoints.

Inclusion criteria:

- 1. Provision of signed and dated informed consent form (ICF)
- 2. Stated willingness to comply with all study procedures and availability for the duration of the study
- 3. Male or female aged ≥ 65 years, living in the community (living at home, able to walk outside from time to time. Homes can include any living community that may or may not offer optional services for the convenience of the residents. Older adults living in nursing homes or in medicalized residences where caretaker services are mandatory are not eligible) and reporting a loss of physical function over the last 6-12 months
- 4. SPPB score ≤ 8
- ALM/BMI < 0.789 in men and <0.512 in women, or ALM < 19.75kg in men and < 15.02kg in women, as measured by DEXA scan
- 6. Ability to take oral medication and be willing to adhere to the study intervention regimen (see section 6)
- 7. Agreement to adhere to the outlined Lifestyle Considerations (see section 5.4) throughout the study duration

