- Various natural substances such as polyphenols (resveratrol, isoflavones), triterpenes (ursolic and oleanolic acid), or phytosteroids (brassinosteroids, phytoecdysones).

Pharmaceutical companies had developed drug candidates based on the above technologies, especially on the use of therapeutic antibodies that inhibit myostatin. They also tested other strategies, in particular the use of testosterone in combination with aromatase inhibitors or receptor SARMs, but the development of these drug candidates was stopped in Phase 2 because of side effects and associated cancer risks. Moreover, SARMs have shown no advantage over testosterone.¹⁷. Finally, clinical research centers specialized in aging have tested the benefit of ACE inhibitors to increase muscle quality and mobility of elderly patients treated for hypertension, and the initial results were promising²⁰.

Regarding clinical research on myostatin inhibition for targeting sarcopenia, two main strategies are used, either blocking the myostatin receptor (activin A/B) or directly blocking myostatin and therefore preventing its interaction with its receptor. Three products have completed Phase 2 studies. These are bimagrumab developed by Novartis, LY2495655 by Ely Lilly, and REGN1033 by Regeneron.

using their Troponin activator (CK-2127107), continue to target sarcopenia as well. The latter study with the troponin activator was terminated due to a lack of efficacy determined during interim analysis.

Bimagrumab **Example 1** is a human monoclonal antibody that binds to myostatin receptor. The phase 2 clinical trial in patients with sarcopenia showed no change in bimagrumab treated group versus placebo. Only a subsequent analysis of the clinical data revealed that sarcopenic participants with slow walking speed showed statistically significant improvements in gait speed and in the 6MWT compared to placebo²¹. However, these results from very limited cohorts did raise concerns regarding correlation between muscle size and function²².

The anti-myostatin antibody, LY2495655, in a phase 2 study on older, weak fallers for 24 weeks²³, induced a significant difference in appendicular lean body mass of 0.43 kg (95% CI 0.192 to 0.660; p<0.0001) but did not show any significant difference compared to placebo with regards to physical performance (stair climbing, chair rise with arms and fast gait speed).

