 To assess changes in body composition and specifically on appendicular lean body mass, which is an expression of sarcopenia. To estimate the change of 400MW test as a dichotomous variable, for possible use in further studies. To evaluate the effects of two daily doses of BIO101 versus placebo on 	Change from baseline of ALM and other parameters of body composition based on DEXA measurements. The rate of success for completing the 400MWtest after the 6-month treatment versus placebo. Change from baseline of the distance during the 6 MWT. Change from baseline of muscle strength based on the knee extension and the SCPT.	Change of body composition and specifically the lean body mass as a proxy for change of muscle mass is an important parameter to measure with respect to the expected mechanism of action of the investigational drug, although many confounding factors can limit the use of this endpoint in a clinical trial. Change in muscle strength is directly related to the expected mechanism of action of the investigational drug and need to be assessed.

OBJECTIVES					
	ENDPOINTS	JUSTIFICATION FOR ENDPOINTS			
mobility functions as	Change from baseline of the	High variability and several confounding			
measured by the distance	The second se	factors can limit the use of this endpoint			
measured during the 6		in a clinical trial, as for the previous			
minutes walking test.	time for five chair stands as				
4. To estimate the effect					
on muscle strength.	assessment.	Change from baseline of SPPB will			
5. To assess the overall	0	provide an estimate of the overall			
change of the SPPB total	the SarQol, PAT-D and TSD-	clinical impact of treatment on the			
score as a cumulative	OC auto-evaluation	burden of physical frailty.			
expression of the physical	questionnaire.	Improvement of the SPPB observed in			
frailty status.		the active intervention group in the LIFE			
6. To assess muscle		study ¹⁶ was mostly explained by the			
functions using a		chair stand test, while the balance test			
simplified function test,		and 4-meter gait speed were only			
i.e. the change in time		slightly modified.			
needed to complete the					
chair stand test.		Change in SarQol PAT-D and/or TSD-OC			
7. To estimate the effect		will provide an estimate of the clinical			
using a sarcopenia-		impact of treatment on sarcopenia			
specific PROs, in		related symptoms from the			
preparation of future		participants' (subjective) perspective.			
studies.					
		- 14			

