In SARA-INT, the definition of the muscle mass component of sarcopenia is based on the operational criteria proposed by the FNIH initiative². FNIH reports triggered a re-appraisal of existing operational definitions of sarcopenia, such as the one from the EWGSOP, that were mostly based on experts' consensus. The new findings of the FNIH relied on a meta-analysis of eleven clinical trials with men and women \geq 65 years. Applying the Classification and Regression Tree (CaRT) statistical model allowed for testing of several variables that best predicted low gait speed and weakness which are the two functional consequences of age-related sarcopenia.

The FNIH project report recommended two alternative gender-specific measures to be used to define low muscle mass². The first FNIH definition, ALM-to- BMI ratio or ALM/BMI, is the one recommended by the FNIH project, while the second definition using the ALM alone is proposed as an alternative.

DEXA scan examination should be performed during the later phase of the screening period after the SPPB assessment. This should be performed only if most of the screening procedures, with the exception of the ultrasound and the 400MW test, have passed the inclusion criteria.

DEXA is a simple, quick and non-invasive examination. DEXA scans can provide accurate measurements of body composition, recording fat and lean mass distribution throughout the entire body. Radiation exposure for the participant is relatively low, approx. 0.0042 mSv for an adult scanned on the Hologic Discovery A device⁴².

DEXA exams will be standardized through the study participating centers.

400 Meter Walk (400MW) Test

The 400MW test is a measure of how long it takes a participant to walk a distance of 400 meters. In addition, the need for each participant to stop and rest (yes/no) and the ability to complete the test at all (yes/no) are factored in as variables. Since the gait speed measured during the 400MW test is defined as the primary endpoint, it is imperative to perform the 400MW test as the last test during the screening period, on Day 0 (prior to randomization) or within 48 hrs of Day 0, in order to ensure data accuracy.

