9.4.8 SUBGROUP ANALYSES

A predefined subgroup efficacy analysis will be performed in a number of pre-identified, at-high risk of worsening, subpopulations:

- Low gait speed
- Sarcopenic obesity
- Study participants with a chair stand sub-score of ≤2 of the SPPB
- Study participants who experience a deterioration in their ALM/BMI as measured by the DEXA scan in the M6 visit compared to the baseline measurement

The subgroup analyses based on these factors will be performed in order to better characterize treatment benefits in patients with increased risk of mobility disability. Results will be presented in forest-plots graphs, for both the primary endpoint and the 2 key secondary endpoints. Parameters of low gait speed (4-meter walk with a gait speed ≤ 0.8 m/s) and sarcopenic obesity (having a percentage of body fat mass of >25% in men and >35% in women) will be used as stratification factors, as well as important demographics or baseline characteristics such as gender, age, country, etc.

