4.2 Secondary endpoints

The key secondary endpoints of this study are:

- Change from baseline to M6/M9 in Physical Function Domain (PF-10) sub-score of the Short Form Health Survey (SF-36)
- Change from baseline to M6/M9 in Handgrip strength test

The other secondary endpoints of this study are:

- Change from baseline of ALM and other parameters of body composition based on DEXA
 measurements
- The rate of success to complete 400 meter walking test after the 6-month/9-month treatment versus placebo
- Change from baseline of the distance during 6 Minute Walking Test (6MWT) distance
- Change from baseline in muscle strength based on the knee extension and the SCPT
- Change from baseline of the SPPB total score
- Change from baseline of the time for five chair stands as part of the SPPB assessment
- Change from baseline using the SarQol auto-evaluation questionnaire
- Change from baseline in PAT-D.
- Change from baseline in TSD-OC for obese patient
- Change from baseline in SF36 (total score)

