8.9 Other analysis

8.9.1 Subgroup analysis

The subgroup analyses will use the FAS.

Subgroup analyses will be performed for the primary endpoint (change from baseline in 400MW gait speed at M6/M9) and the key secondary endpoints (change from baseline in PF-10 sub-score of the SF-36 and change from baseline to M6/M9 in Handgrip strength test).

Version Final 2.0, Date: 04JUN2021

Page 44 of 69

These pre-identified, at-high risk of worsening, subpopulations have been identified:

- Low gait speed (4 meter walk with a gait speed <= 0.8 m/s) at Screening
- Sarcopenic obesity (having a percentage of body fat mass of >25% in men and >35% in women) as measured by the DEXA at Screening
- Study subjects with a chair stand sub-score of ≤2 of the SPPB at Screening
- Study subjects who experience a deterioration. Deterioration is defined as a decrease of > 2% in the ALM or BMI value at M6/M9 compared to the Screening value.

The subgroup analyses based on these factors will be performed in order to better characterize treatment benefits in subjects with increased risk of mobility disability. The analysis will be performed in both the subpopulations identified above and the group of FAS patients that are not in the subgroup. Summaries of each subgroup by treatment will be presented and MMRM analysis per section 8.7.1.1 will be performed for the primary endpoint and PF-10. An ANCOVA method detailed in section 8.7.1.12 will be used for the analysis of change from baseline to M6/M9 in Handgrip strength test. Parameters of gait speed (400MW with a gait speed <= 0.8 m/s/400MW with a gait speed > 0.8 m/s) and sarcopenic obesity (percentage of body fat mass of >25% in men and >35% in women/ percentage of body fat mass of \leq 25% in men and \leq 35% in women) will be included in the models. Important demographics or baseline characteristics such as age, country, etc. may be defined prior to the database lock and unblinding and will be included in the model.

Least square mean difference (175mg BIO101 Vs Placebo and 350mg BIO101 Vs Placebo) and 95% CIs for each of the subgroups will be presented in forest-plots.

No adjustment for multiplicity will be performed.

A by-subject listing will be provided.

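### SAP 8.9.1 analyses a subgroup defined by change after randomisation as if it were a baseline subgroup, and replaces the protocol's ALM/BMI ratio with a fall in either ALM or BMI without declaring it

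*SAP*

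**What the plan says.** SAP 8.9.1 lists four subpopulations thought to be at high risk of decline. Three (slow 4-metre gait, sarcopenic obesity, low chair-stand sub-score) are fixed at Screening. The fourth is participants who deteriorate: "Deterioration is defined as a decrease of > 2% in the ALM or BMI value at M6/M9 compared to the Screening value". Gait speed, PF-10 and handgrip are analysed by treatment within each subgroup and within "the group of FAS patients that are not in the subgroup". The differences from placebo, with 95% CIs, go into forest plots without multiplicity adjustment.

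Protocol 9.4.8 describes the fourth group as "Study participants who experience a deterioration in their ALM/BMI as measured by the DEXA scan in the M6 visit compared to the baseline measurement". The synopsis has nearly the same words: "Study participants who experience a deterioration in their ALM/BMI, as measured by the DEXA scan, in the M6 visit compared to the baseline measurement". Neither gives a threshold. ALM/BMI in the protocol is a ratio; section 8.1 says of the ALM-to-BMI measure that "ALM/BMI, is the one recommended by the FNIH project".

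ALM is also an outcome. SAP 4.2 lists among the other secondary endpoints: "Change from baseline of ALM and other parameters of body composition based on DEXA". Protocol section 3 says that lean body mass "is an important parameter to measure with respect to the expected mechanism of action of the investigational drug".

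The SAP's list of changes from the protocol declares the move from M6 to M6/M9. It mentions neither the either-component rule nor the 2% cut.

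**The concern.** A treatment comparison inside a subgroup is protected by randomisation only if treatment cannot influence who is in it. Here membership is read off after six to nine months of treatment, from a measure the drug is meant to affect. Suppose the drug preserves lean mass. Those on drug who still lose more than 2% are then a more adversely selected set than those on placebo who do. The people kept out of the subgroup by the drug join the complement and change its make-up too. Both contrasts then compare unlike groups. In the forest plot they look the same as the three subgroups that are free of this problem.

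The definition is a separate matter. BMI is the denominator of the protocol's ratio, so losing weight with stable lean mass improves the ratio. The SAP rule calls that deterioration.

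At stake is how the subgroup plots are read, since their stated purpose is to characterise benefit in people at greater risk.

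**Working it through.** **The plan's own figure.** The documents give no expected size or power for this subgroup. The only related figure is 64 per arm (Protocol 9.2: difference 0.1 m/s, SD 0.20, two-sided 0.05, power 80%). Normal formula: 2 × (1.960 + 0.842)² × (0.20/0.10)² = 62.8, so 63; the t-based solution is 63.77, so 64. It reproduces and is used below only for scale.

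**Do the two rules agree?** Ratio change = (1 + ALM change)/(1 + BMI change) − 1.

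| ALM | BMI | Ratio change | SAP rule | Protocol ratio |
|---|---|---|---|---|
| 0% | −3% | 1/0.97 − 1 = +3.1% | deteriorated | improved |
| −1% | +3% | 0.99/1.03 − 1 = −3.9% | not deteriorated | deteriorated |

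The rules can point in opposite directions, and no choice of threshold on the ratio removes the first contradiction.

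**How large could the selection bias be?** The documents give none of the needed inputs except the gait SD of 0.20. Everything else is assumed. With x and u independent standard normal:

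- ALM % change = −1 + d + sa·x
- BMI % change = b + sb·(r·x + √(1 − r²)·u)
- expected gait change = 0.20·(ρ·x + γ·u), identical in both arms, so the true drug effect on gait is zero

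Here d and b are the drug effects on ALM and BMI in percentage points. Grid: sa 3 or 4; sb 3, 3.5 or 4; r 0.3, 0.5 or 0.7; ρ 0.1, 0.3 or 0.5; γ −0.2, 0 or +0.2. Bias is the drug mean minus the placebo mean, taken among those meeting the SAP rule and among those not meeting it.

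| Drug effect | γ | Subgroup (m/s) | Complement (m/s) |
|---|---|---|---|
| none | any | 0 | 0 |
| ALM +1 point | 0 | −0.008 to 0.000 | −0.016 to −0.002 |
| ALM +2 points | 0 | −0.012 to +0.001 | −0.028 to −0.004 |
| ALM +2 points | −0.2 to +0.2 | −0.025 to +0.015 | −0.030 to −0.001 |
| BMI −1 point | −0.2 to +0.2 | −0.001 to +0.016 | −0.006 to +0.010 |

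These are extremes over the grid, not bounds. One setting with opposite signs: sa 4, sb 3.5, r 0.5, ρ 0.3, γ −0.2, d +2 gives +0.006 in the subgroup and −0.015 in the complement. Membership there is 50% on placebo and 39% on drug.

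For scale, if half of 64 per arm are in the subgroup, its 95% CI half-width is 1.96 × 0.20 × √(2/32) = 0.098 m/s. The subgroup's largest value, 0.025, is about a quarter of that (0.025/0.098 = 26%).

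**Would the ratio cure the bias?** No. With a 2% cut on the ratio, d = +2 and γ = 0, the ranges are −0.036 to −0.001 in the subgroup and −0.022 to −0.001 in the complement.

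**Misclassification on placebo** (base case sa 4, sb 3.5, r 0.5; grid range in brackets). Of those the SAP calls deteriorated, 33% (22–46%) have a higher ratio. Of those whose ratio falls by more than 2%, the SAP rule misses 35% (28–59%).

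**Who is left unplaced?** SAP 7.1.1 derives BMI from weight and height, and the protocol's schedule lists anthropometry separately from DEXA at the end visit. Someone with no second scan but an end-visit weight showing a BMI fall above 2% therefore meets the SAP rule. Those for whom neither criterion can be shown met, for example with no second scan and no end-visit weight, fall by default into the complement. DEXA, the 400-metre walk and grip share the end visit, so this matters mainly for PF-10, which was also collected by telephone, and for M3 data in the MMRM.

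**The case against.** The best defence is that the SAP did not invent this subgroup. A reader might infer from 8.9.1 that it introduced membership set after randomisation. The documents do not support that: the protocol had already defined the group by the M6 scan and asked for forest plots, and the SAP declared the move to M6/M9. This changes where the problem began but does not remove it.

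A reader might also count the 2% cut as an undeclared departure. That is too strong. The protocol leaves deterioration undefined, and giving it a threshold is ordinary SAP detail. The either-component rule cannot be defended this way, because it reverses the role of BMI. It may be a drafting slip: SAP 8.7.3.2 lists ALM BMI, without an operator, among the DEXA parameters. A programmer working from 8.9.1 would still code what it says.

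Third, the bias figures rest on assumptions. The link between lean mass and function is itself uncertain: the protocol notes that results for another agent "did raise concerns regarding correlation between muscle size and function". No passage predicts a drug effect on BMI. This stands, so the figures show only that the bias can be non-zero and can change sign.

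Finally, this is one supportive, unadjusted subgroup among four. That limits the consequence and is reflected in the verdict.

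**Conclusion.** The point holds, with moderate weight. The wording should be changed before unblinding because, followed literally, the SAP yields two non-randomised contrasts presented as ordinary subgroup effects, in a group that can include people the protocol would call improved.

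The selection bias is conditional. It needs a treatment effect on ALM or BMI and a correlation of those changes with outcome. Under the assumed inputs it is a modest part of the subgroup's sampling error, and its sign is not fixed, so a reader could not correct for it. It would be wrong to infer that the results will favour, or disfavour, the drug. It would also be wrong to infer that everyone without a second scan drops into the complement, or that restoring the ratio would make the comparison a randomised one. The contradiction between the two definitions is arithmetic and needs no assumption; only its frequency does.

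The primary test, the Hochberg procedure and the sample size are untouched.

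**What to change.** In SAP 8.9.1, take this item out of the baseline treatment-effect subgroups and their forest plots.

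If it is kept because the protocol lists it:

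- define it by the protocol's ALM/BMI ratio, with one threshold fixed before unblinding (for example the SAP's own 2%);
- limit both it and its complement to participants with both scans;
- show it separately, labelled descriptive and non-randomised.

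In either case, report ALM/BMI deterioration by arm as an outcome under the same rule, with the number per arm lacking a second scan, and record the change in the SAP's list of changes from the protocol.

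The cost is SAP wording, one entry in that list, and the loss or downgrading of one exploratory comparison.

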> The study plan is divided into: a) screening and randomization phase and b) treatment and evaluation phase. The recruitment lasts approximately 24 months. The investigational phase initially comprises three main visits for measurement of drug efficacy, pharmacokinetics (when appropriate) and safety parameters: 1) the inclusion visit, 2) the 3-month evaluation and 3) the 6-month final evaluation visit. Additionally, three communications (visit and phone calls) were planned for safety measures only: 1) an on-site visit at 1-month after randomization, 2) a telephone call at 5-month after randomization, and 3) a telephone call 6 weeks post drug intervention (i.e. after M6 visit) or after the end-of-intervention visit.

The primary outcome is the change from baseline in gait speed, in meters per second (m/s), between the treatment groups versus placebo based on the 400 meters walking (400MW) test.

The Short Form Health Survey (SF-36) and two other patients reported outcomes (PROs) will be completed by the participants on inclusion day (Day 0), at the month 3 (M3) visit and the month 6 (M6) or end-ofintervention visit. The Physical Function Domain (PF-10) sub-score of the SF36 at M6 will be tested as a key secondary outcome at M6. Additionally, the change from baseline of muscle strength measured by the handgrip strength test will be used as another key secondary outcome. Additionally, the SPPB will be evaluated at each visit and the 6 Minute Walk Test (6MWT) will also be administered during the two main visits (Day 0 and M6) and considered as part of the secondary criteria at M6.

At any time, participants complaining of meaningfully worsening of physical functions may be invited to an unscheduled visit for further assessment for consideration of their continued participation in the study.

The statistical analyses will describe the demographic and functional characteristics of the three treatment groups at baseline, and compare the evolution (change in each treatment group versus placebo group) of the primary, key secondary, secondary and exploratory endpoints. The evolutions of efficacy parameters will also be analyzed according to specific variables or class of variables, e.g. gender, age, initial SPPB score, ALM, ALM/BMI and etc, in view of identifying a subpopulation at high risk of worsening and/or to show the homogeneity of the treatment effect across subgroups.

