4 STUDY DESIGN

4.1 OVERALL DESIGN

SARA-INT is a 3-arm (2 doses versus placebo), randomized, double-blind, placebo-controlled parallel design phase 2 clinical trial. This comparative clinical trial evaluates the effects of a 6-month treatment duration, based on the hypothesis that physical function of sarcopenic, older patients with an initial degree of mobility disability (SPPB≤8) will be meaningfully improved after 6 months of oral treatment with BIO101 (in at least one of the two tested doses) with respect to placebo.

SARA-INT is a multi-site study that aims to enroll 231 community dwelling, older adults (men or women \ge 65 years), reporting a loss of physical function over the previous 6-12 months, and at risk of mobility disability, to undergo screening tests for inclusion in the study. Included participants will be randomized in a 1:1:1 ratio, for one of the 3 arms of treatment in a blinded manner. The randomization will be stratified by gender and by center. Bias are minimized by the use of identical therapeutic units whose number is automatically assigned via an eCRF embedded algorithm after the Investigator confirms randomization of a participant. All included participants will complete the inclusion visit and start a 6 to 9-month treatment and observation, with the main evaluation at the end of the study duration. Based on non-clinical safety considerations, the investigational drug exposure is capped at 39 weeks. The complete Schedule of Activities is provided in Section 1.3.

An interim analysis will take place however, the number of completers, based on which it will be conducted, will be determined once restrictions are lifted and it is clear, how many participants dropped out before the end-of-study assessments.

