9.2 SAMPLE SIZE DETERMINATION

Originally, the sample size was calculated for a comparison test at a 0.05 two-sided significance level, a power of 80%, to detect a difference of 0.05 m/s (minimal clinically important difference) between active groups and placebo on the change from baseline in the 400 m gait speed at 6 months, with a standard deviation of 0.13 (estimated from the VIVE2 trial, Fielding et al, 2017⁶²).

After analysis of the preliminary data from our observational trial data (SARA-OBS, with approx. 105 completers), the following were learned:

- During the 6 months follow-up, this study population deteriorated as suggested by a decreased gait speed of 0.05 meter per second on the 400MW test, with a standard deviation of the change from baseline of 0.2
- The expected effect of BIO101 remains at 0.05 meter per second, as the change from baseline
- Together, this new information allows an increase of up to 0.1 m/s to be considered as a minimal clinically important difference of changes at the M6 visit from baseline between the treatment groups. Under these assumptions, a number of 64 patients/group is needed, giving a new sample-size of 192 patients for 3 arms, with a standard deviation of 0.20 (estimated from SARA-OBS preliminary data).

Taking into consideration this increased expected difference between treatment arms, a formal interim analysis will be performed by the DSMB when half subjects reach their month 6 visit (See section 9.4.6). Once half study participants complete their End-of intervention study visit, an unblinded 'promising zone' interim analysis will take place and determine if there is a need to increase the sample size based on the complete efficacy data.

Based on current calculation and given a limited 20% provision for premature withdrawals or lost-to-follow up, a total number of 231 participants will be included in the study.

It is expected, that due to COVID-19 related restrictions, that the number of non-evaluable withdrawals will be higher than 20%. However, reassessment of the sample size, will take place, as a part of the interim analysis, that will take place after restrictions are lifted.

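### No treatment-by-subgroup contrast is pre-specified for the synopsis aim of homogeneity; separately, the low-gait-speed factor is defined on two different walking tests

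*SAP*

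**What the plan says.** **Subgroup estimation.** SAP 8.9.1 states: "The analysis will be performed in both the subpopulations identified above and the group of FAS patients that are not in the subgroup". It uses the MMRM of SAP 8.7.1.1 for gait speed and PF-10 and the ANCOVA of SAP 8.7.1.2 for handgrip. Differences from placebo with 95% CIs go into forest plots, without multiplicity adjustment.

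**Interactions.** The MMRM contains treatment by visit and no other interaction. The ANCOVA has main effects only. Protocol 9.4.1 excludes interactions by default and provides for further analyses, not described, if the subgroup results prove interesting.

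**Purpose.** The protocol synopsis (1.1) gives two aims joined by and/or. One is to find a subpopulation at high risk of worsening; the other is "to show the homogeneity of the treatment effect across subgroups". Protocol 9.4.8 and SAP 8.9.1 give a different purpose: describing benefit more closely in people at greater risk of mobility disability.

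**Gait-speed factor.** The subgroup list in SAP 8.9.1 defines low gait speed by the 4 m walk at screening, at or below 0.8 m/s. The term put into the models in the same section is "Parameters of gait speed (400MW with a gait speed <= 0.8 m/s/400MW with a gait speed > 0.8 m/s". Protocol 9.4.8 has "Parameters of low gait speed (4-meter walk with a gait speed ≤ 0.8 m/s". The SAP's list of changes from the protocol does not mention the switch. A sarcopenic obesity term also goes into the models.

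**The concern.** Subgroup and complement will sit next to each other on a forest plot, each with its own estimate and interval, and no planned quantity compares them. Readers will tend to compare significance: an interval that excludes zero in one group and not in the other will be taken as a differential effect. The only route to an interaction analysis opens after the results have been seen.

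The risk is concrete. The protocol's own background (2.1) describes a phase 2 trial of a myostatin-receptor antibody with no overall effect, in which a later analysis reported benefit in slow walkers. Low gait speed is the first subgroup listed here.

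The gait-speed factor is a second, unrelated fault. Protocol 8.1 itself says that the 400 m walk picks up people whose limitation does not show on shorter tests such as the 4 m walk, so the two cuts at 0.8 m/s do not define the same group. In the primary model the 400MW cut also splits into two a quantity that is already a continuous covariate: SAP 8.7.2 takes the screening 400MW speed as baseline, and SAP 8.7.1.1 puts baseline in the model. (SAP 8.9.1 does not give the visit for the 400MW cut; screening is assumed.)

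**Working it through.** **Inputs**
- Effect: 0.1 m/s. Protocol 9.2: "this new information allows an increase of up to 0.1 m/s to be considered as a minimal clinically important difference".
- SD and size: Protocol 9.2: "a number of 64 patients/group is needed, giving a new sample-size of 192 patients for 3 arms, with a standard deviation of 0.20".
- Allocation: Protocol 4.1: "Included participants will be randomized in a 1:1:1 ratio".
- Alpha and power: Protocol 9.2, for the original calculation: "the sample size was calculated for a comparison test at a 0.05 two-sided significance level, a power of 80" per cent. These are not restated for the revised calculation and are assumed to carry over.
- Subgroup share f: not given in the documents. Assumed 50%, 30% and 20%.

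**Step 1: the plan's own figure.** n per arm = 2 × (1.960 + 0.842)² × 0.20² / 0.1² = 62.8, so 63 by the normal approximation. The exact t-test gives 64 (power 80.1%). The stated 64 is reproduced. The total of 231 is 192 × 1.2 = 230.4 rounded up, or 77 per arm.

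**Step 2: standard errors, one dose versus placebo, 64 evaluable per arm.**
- Overall: 0.20 × √(2/64) = 0.0354.
- Within a half-sized subgroup (32 per arm): 0.20 × √(2/32) = 0.050, which is 1.41 times the overall value.
- Contrast between subgroup and complement: 0.20 × √(2/(64f) + 2/(64(1−f))). At f = 50% this is 0.0707, twice the overall value.

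**Step 3: side-by-side significance when the effect is the same everywhere (0.1 m/s).** Power in a group is approximately Φ(0.1/SE − 1.96). At f = 50%: Φ(2 − 1.96) = 0.516 in each half. The chance that exactly one is significant is p₁(1 − p₂) + p₂(1 − p₁) = 2 × 0.516 × 0.484 = 0.499.

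| Share f | Power in subgroup | Power in complement | Exactly one significant |
|---|---|---|---|
| 50% | 0.516 | 0.516 | 50% |
| 30% | 0.341 | 0.658 | 55% |
| 20% | 0.244 | 0.716 | 61% |

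By construction, a 5% interaction test would signal a difference in 5% of such trials.

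**Step 4: what an interaction analysis can deliver.** At f = 50%, power for an interaction of 0.1 m/s is Φ(0.1/0.0707 − 1.96) = Φ(−0.546), about 0.29. The difference detectable with 80% power is 2.80 × 0.0707 = 0.198.

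| Share f | SE of interaction | Power for 0.1 m/s | Detectable at 80% | 95% CI half-width |
|---|---|---|---|---|
| 50% | 0.071 | 29% | 0.20 | 0.14 |
| 30% | 0.077 | 25% | 0.22 | 0.15 |
| 20% | 0.088 | 20% | 0.25 | 0.17 |

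If all 77 per arm were evaluable, power would be 34%, 30% and 24%. An interaction of 0.1 m/s at 80% power would need about 252, 300 and 393 evaluable per arm.

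**Step 5: the gait-speed texts side by side.** The SAP subgroup uses 4 m. The protocol factor uses 4 m. The SAP model term uses 400 m. All three use the 0.8 m/s cut. Only the third differs, and it is not declared. No arithmetic is needed.

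**The case against.** The strongest reply has five parts.

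1. *The homogeneity aim belongs elsewhere.* The synopsis attaches it to variables such as gender, age, SPPB score and lean mass, as one of two alternatives, and introduces the at-risk subpopulations afterwards with another purpose. This stands, and it limits how much can rest on the aim. It does not supply a planned analysis: SAP 8.9.1 mentions age and country only as possible model terms.
2. *The comparison can be recovered.* A reader might infer that homogeneity cannot be examined at all. The documents do not support that. Subgroup and complement contain different people, so the contrast is the difference of the two estimates with SE = √(SE₁² + SE₂²), both from planned output. What is missing is the commitment to report it.
3. *Leaving interactions out is a deliberate default in a phase 2 trial, with a follow-up route.* The default is defensible. The follow-up is unspecified and triggered by the results.
4. *An interaction p-value would not show homogeneity.* This is correct at 20–29% power, and it is why the estimate with its interval should be the main output. A joint model does not remove the doubled standard error, which comes from sample size.
5. *The side issues are harmless.* A sarcopenic obesity term inside its own subgroup or complement is constant and aliased with the intercept; the treatment contrast is unchanged, so the term is redundant and causes no bias. Worries about unstable small models are eased by the fallback covariance structures (SAP 8.7.1.1) and the pooling of centers (SAP 8.7.1.8).

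**Conclusion.** The point holds in two separate parts, both minor in severity.

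First, no treatment-by-subgroup estimate or test is pre-specified, so the synopsis aim of homogeneity has no planned analysis. Under a uniform 0.1 m/s effect, comparing significance would suggest a difference in about 50% to 61% of trials over the assumed shares.

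Second, the low-gait-speed factor is inconsistent within SAP 8.9.1 and departs from Protocol 9.4.8 without being listed. A reader might infer that this mismatch is what defeats the homogeneity aim. It does not: an adjustment covariate does not decide whether subgroups can be compared.

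The figures assume independent groups, SD 0.20 and no covariate adjustment, which would raise power somewhat. They cover one dose versus placebo and are not corrected for two doses, several subgroups or three endpoints.

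**What to change.** - For each of the three baseline-defined factors (low gait speed, sarcopenic obesity, chair-stand sub-score), fit one model on the FAS. Use treatment × subgroup × visit with all lower-order terms for gait speed and PF-10, and treatment × subgroup for handgrip. The deterioration subgroup is defined after randomization and is outside this proposal.
- On the forest plot, add the interaction estimate at M6/M9 with its 95% CI for each dose (p-value optional), labelled exploratory. State that power is about 29% for a 0.1 m/s interaction with a half-sized subgroup and 64 per arm, lower for smaller subgroups, and that a non-significant result does not show homogeneity.
- Use the protocol's 4 m definition wherever the low-gait-speed factor appears, or list and justify the departure in the SAP's changes section.
- Remove the 400MW dichotomy and any subgroup term that is constant within the set analysed.

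The cost is a short SAP amendment before unblinding and a small programming change. The joint model assumes common covariate effects and a common covariance across subgroup levels, unlike the separate fits. The low power remains and has to be reported.
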